Clinically, HAs precipitated by trauma do not have unique defining characteristics and are treated empirically based on their resemblance to primary HA disorders. In the civilian TBI population, for whom injury is by far most often due to mechanisms other than blast, PTHAs tend to be tension-type, migraine, or mixed, whereas in the military combat population, particularly in the setting of blast TBI and physical injury, HAs with migraine features predominate. These blast-related PTHAs seem to be more refractory to standard prophylactic pharmacotherapies than those following non-blast TBI, as demonstrated in a retrospective cohort study evaluating medical treatments of PTHAs in SMs conducted by study Consultant, COL [name], at the Madigan Neurology Clinic. HA frequency was determined at initial clinic visit and again at 3 months after starting HA prophylactic medications. Only 29% of blast-TBI PTHA patients compared to 57% of non-blast TBI PTHA patients had a 50% or greater decline in HA frequency (P=0.023) with treatment. This reduced rate of response is concerning for an increased risk for development of long-term HA persistence (chronification). This concern is supported by findings from a recent cross-sectional study. Among 978 soldiers with deploymentrelated concussion, 20% met criteria for chronic daily HA (at least 15 HAs per month), which is 4- to 5fold higher than that seen in the general population. In this group, 66% had HA with migraine features. Chronic daily HA, particularly with migraine features, is considered to be one of the most disabling and difficult to treat HA syndromes.

HA disorders are one of the top reasons for military disability evaluation. Theeler et al found that migraine HAs tended to persist after return from deployment, and were associated with substantial disability. Seventy-seven percent of all migraine attacks interfered with duty performance on a mean of 2.4 days per month. Of particular concern is a recently reported association between migraine and suicide in Veterans. Based on a large-scale retrospective analysis of noncancer pain conditions and risk of suicide in Veterans, the investigators found a suicide mortality hazard ratio of 1.34 (1.02-1.77) for migraine, after controlling for comorbid psychiatric conditions.

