Prazosin may cause syncope with sudden loss of consciousness. In most cases, this is believed to be due to excessive postural hypotension although occasionally the syncopal episode has been preceded by severe tachycardia with heart rates of 120-180 beats per minute. Syncopal episodes have usually occurred within 30-90 minutes of the initial dose. The incidence of the syncopal episodes is 1% if the initial dose is 2 mg or more. Clinical trials suggest that syncopal episodes can be minimized by starting with a dose of 1 mg and slowly titrating up to the final dose, as we are doing in this study.

HA is listed in the Physician Desk Reference as a potential adverse reaction to prazosin, reported in as many of 8% of subjects in early clinical trials. However, in our experience, the incidence of this is lower. In the previously described placebo-controlled pilot study evaluating use of prazosin for treatment of PTSD in Iraq and Afghanistan active-duty SMs in which HA was monitored as a potential side effect of prazosin, 22 of 26 participants had HA at baseline. Among those randomized to prazosin, 1 of the 22 with baseline HA had worsening of their HAs, and 1 of 4 participants with no prior HA history developed HAs. In contrast, 11 of the 22 with baseline HAs had improvement or complete resolution of their HAs while on prazosin. Among those randomized to placebo, 3 of 9 participants with no prior HA history developed HA.

Regarding mood alterations, although depression is listed in the Physician Desk Reference as occurring in 1-4% of patients, we have found little evidence for prazosin precipitating or worsening symptoms of depression. In 33 participants administered the Hamilton Depression Rating Scale (Ham-D) in our recently completed placebo-controlled study of prazosin for PTSD, Ham-D scores actually improved

more in the prazosin vs. placebo group (5.3 vs. 0.7, t=1.9 [2-tailed], p=0.07). However, for safety reasons, participants will be carefully monitored for signs and symptoms of depression and other mood disorders.

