**Risk Management and Emergency Response:** Evaluation for adverse effects and review of concurrent medications will be completed at all study visits. Participants are asked about suicidal ideation at each in-person visit. If endorsed, participants will be assessed as to their level of risk and the level of care required to keep them or others from harm. If a participant requires inpatient treatment in order to prevent harm or is found to have symptoms of disorganized thought processes secondary to psychosis, mental health personnel will be notified immediately to assist with appropriate triage and referral. Vital signs, including orthostatic blood pressure (BP) and heart rate (HR) will be performed at all study visits. Systolic and diastolic BP and HR will be obtained following 10 minutes of rest, and repeated following 2 minutes of standing. Occurrences of lightheadedness, dizziness on standing, palpitations, drowsiness, nausea, nasal congestion, peripheral edema, worsening of HA, and other adverse effects will be rated by the clinician. For vital signs parameters, unacceptable side effects will include resting hypotension (systolic BP<100 mm Hg) and clinically meaningful hypotension (20 mm Hg or more drop in systolic BP accompanied by dizziness, lightheadedness, or syncope).

For participants taking other antihypertensive medications, their primary care provider will be informed of clinically significant BP reductions at any time during the study, to allow adjustment of the participant's antihypertensive regimen. As a further precaution, male subjects will be advised to sit on the toilet for urination the first two nights to avoid orthostatic hypotension secondary to micturition syncope.

Safety monitoring is based on long-term clinical experience with prazosin. Prazosin was first introduced in 1976 under the trade name Minipress (Pfizer) for clinical management of hypertension, and later became widely prescribed for urinary outflow obstruction secondary to benign prostatic hypertrophy. It has been safely prescribed to large numbers of middle-aged and older people over the past 40 years. The following information regarding the side effect profile and safety record of prazosin is a synopsis from the Minipress package insert: "The most important adverse effect to be considered when prescribing

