prazosin is a "first dose effect" manifested by syncope with sudden loss of consciousness believed to be due to postural hypotension in approximately 1% of patients given an initial dose of 2 mg or greater. This rare adverse effect is self-limiting and in most cases does not recur after the initial period of therapy or during subsequent dose titration. However, patients should always be started on 1 mg of prazosin. In clinical trials of prazosin, most frequent adverse reactions were dizziness (10%), HAs (8%), drowsiness (8%), lack of energy (7%), weakness (7%), palpitations (5%), and nausea (5%). Less frequent adverse reactions (1-4%) were: vomiting, diarrhea, constipation, edema, orthostatic hypotension, dyspnea, syncope, vertigo, depression, nervousness, rash, urinary frequency, and nasal congestion. Fewer than 1% of patients have reported the following (causal reactions sometimes not established): abdominal discomfort or pain, tachycardia, paresthesias, hallucinations, pruritus, incontinence, impotence, and priapism..."

Through extensive experience of our group, including open-label clinical studies, placebo-controlled trials, and clinical application, prazosin has demonstrated a favorable safety profile. Several thousand active-duty SMs and Veterans with PTSD have now been treated with prazosin at VA Puget Sound and Madigan, as well as at other centers, including the Spokane, Portland, and Cleveland VA Medical Centers. It has been estimated that over 70,000 Veterans nationwide are being treated with prazosin for PTSD. Approximately 5% of those treated with prazosin have discontinued it secondary to subjectively unpleasant side effects, most commonly transient orthostatic dizziness, nasal congestion, or exercise-induced tachycardia.

Regarding other participant safety issues, procedures relevant to the war-zone trauma and TBI population include exclusion of participants with severe psychiatric instability or severe situational life crises, including evidence of being actively suicidal or homicidal, or any behavior that poses an immediate danger to the participant or others. A female Rater will be available to perform interview-based assessments, if requested by female participants. Trained personnel will be on call at all times to receive calls from participants regarding any adverse events; participants will be provided with 24-hour emergency contact numbers.

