#### **Compensation:**

Veteran participants (at VA Puget Sound and Madigan sites) will be compensated \$100 for each of 2 weeks of actigraphy monitoring and \$50 per in-person study visit to defray transportation costs and inconvenience, up to a total of \$950. In addition, participants may receive a blood pressure cuff to use for remote visits that require an orthostatic vital signs assessment, which participants will keep at the conclusion of their participation. Veterans will be compensated for extra study visits that may be required per clinician judgement (i.e., extra safety visits or extra titration visits). Payments will be prorated, based on the number of completed study visits and weeks of actigraphy. In addition, Veteran participants will be compensated an additional \$25 per visit if they must travel between 50-100 miles round trip and \$50 per visit if they must travel over 100 miles round trip to attend study visits, to defray travel costs.

For visits done remotely (by telephone or telehealth), Veterans will be compensated according to the guidelines below, based on the level of burden placed on the participant per visit:

- Participants will not be paid for the telephone safety checks, such as P1.5, P2.5, and SD3.5 visits.
- For lower-burden visits, such as the P2, P3, T2-T8, and SD1 visits, participants will receive \$20 per remote visit
- For higher-burden visits, such as the P1, T1, and SD2-SD4 visits, participants will receive \$50 per remote visit.

This rate of compensation complies with the VA Puget Sound IRB guidelines for prevention of research study participant financial coercion.

Active-duty and Federal Personnel participants at Madigan: Per Section 30 of Title 24, U.S.C.:

- Active-duty SMs and Federal personnel cannot be reimbursed for any of the study procedures, except for \$50 compensation if a blood draw is performed. In this study, Madigan participants may have one blood draw if laboratory evaluations are clinically indicated.
- SMs and Federal personnel while off duty may be compensated for research participation other than blood draws in the same way as human subjects who are not Federal personnel. If a Madigan participant is off duty while completing study procedures, they will be compensated as detailed for VA Puget Sound participants above.

All payments will occur through one of the foundations overseeing the grant. No payments will be made directly by a government source.

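### The suicidal-ideation question is required only at in-person visits, although the protocol lets every visit be held remotely

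*Combined protocol and SAP*

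**What the plan says.** Under Foreseeable Risks, section 5.1 commits that "for safety reasons, participants will be carefully monitored for signs and symptoms of depression and other mood disorders". It names no instrument, visit or frequency for this.

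Under Risk Management and Emergency Response, the same section requires evaluation of adverse effects and measurement of vital signs at every visit. The ideation question has a narrower scope: "Participants are asked about suicidal ideation at each in-person visit". If a participant endorses ideation, the level of risk and the care needed are to be assessed. The Schedule of Study Visits has no row for the question, so this sentence is the only place that fixes when it is asked.

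Section 5.5 (Procedures to minimize missing data) permits all visits, in whole or in part, to be remote for reasons of safety or burden. It says in general terms that adverse-event queries and the remaining assessments are then done remotely.

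The Compensation text in section 5.2 shows that remote visits are planned for. It has a $20 remote rate ("For lower-burden visits, such as the P2, P3, T2-T8, and SD1 visits, participants will receive") and a $50 remote rate ("For higher-burden visits, such as the P1, T1, and SD2-SD4 visits, participants will receive"). A third group is by telephone by design: "Participants will not be paid for the telephone safety checks, such as P1.5, P2.5, and SD3.5 visits".

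**The concern.** Read literally, the one scheduled question that asks directly about suicidal thoughts drops out when a visit moves to telephone or telehealth. Adverse-effect review does not. Other checks were adapted for remote use: home blood-pressure cuffs are provided, and pregnancy tests can be mailed and verified by telehealth. The ideation question has no such rule, and two sites following the same text could act differently.

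The protocol itself gives the reason to care. The Introduction says: "Of particular concern is a recently reported association between migraine and suicide in Veterans", and cites a suicide-mortality hazard ratio of 1.34 (1.02 to 1.77) for migraine. That background risk concerns both arms. Only severe depression is excluded, so milder depression can be enrolled. Development of an unstable psychiatric condition is a ground for ending participation (section 5.7), but it has to be detected first.

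**Working it through.** The plan states no figure to reproduce. The check is a comparison of texts and a count of visits.

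**Inputs.** First dose: the evening of T1 (section 5.5). Titration: 5 to 7 weeks (section 5.1). Outcome scales are repeated at steady-dose weeks 4, 8 and 12, which are SD2, SD3 and SD4. PHQ-9 in the schedule: P1, T1, SD2, SD3 and SD4, and blank at T2-T8 and SD1. Outcome-visit window: 14 days either side.

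**Interval from first dose to the next PHQ-9.**
- Nominal: 5 + 4 = 9 weeks, up to 7 + 4 = 11 weeks.
- With the window: 9 − 2 = 7 weeks, up to 11 + 2 = 13 weeks.
- Visits inside it: T2-T6 (5) + SD1 (1) = 6; with T7 and T8, 8.
- Total daily dose from the titration table: 1, 2, 5, 8, 15, 20, 25 mg. That is six increases, on days 3, 8, 15, 22, 29 and 36. None is allowed after the steady-dose period starts, so all six fall in this interval.

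**Scheduled visits after the first dose.** T2-T6 (5) + SD1, SD2, SD3, SD3.5 and SD4 (5) = 10; with T7 and T8, 12.

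| How visits are held | Ideation question required | PHQ-9 scheduled |
|---|---|---|
| All clinic visits in person (SD3.5 by telephone) | 10 − 1 = 9 of 10, or 12 − 1 = 11 of 12 | 3 |
| Titration visits and SD1 remote, SD2-SD4 in person | 10 − 6 − 1 = 3 of 10, or 12 − 8 − 1 = 3 of 12 | 3 |
| All remote | 0 of 10, or 0 of 12 | 3 |

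The three PHQ-9 administrations (SD2, SD3, SD4) do not depend on visit mode, since self-rated forms can be sent to participants. However, remote forms may come back by mail or at the next in-person visit, and the documents attach no risk assessment to a PHQ-9 answer. The three all fall at or after steady-dose week 4, so none covers the titration interval.

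**The case against.** The strongest reply is that section 5.5 is the specific rule for remote visits. It provides for telephone or telehealth versions of assessments and then lists what may be skipped: biomarker blood draws, the pupillary reflex and, by telephone only, the MoCA. The ideation question is not on that list. On this view a remote clinic visit keeps its content, and the in-person wording merely separates clinic visits from the short telephone checks. This is a fair reading of intent, and it makes the problem an ambiguity rather than a deliberate omission. It does not settle the text. Section 5.1 states an explicit limit, next to sentences that cover every visit, and section 5.2 uses in-person as the opposite of remote.

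A reader might also infer that a remotely seen participant has no mood safeguard at all. The documents do not support that. Severe depression and active suicidality are excluded at entry. Adverse effects are queried by staff at every visit after the first dose, including the week-11 telephone check. Section 5.7 provides for triage to mental health support at any time. Section 5.1 adds: "Trained personnel will be on call at all times to receive calls from participants regarding any adverse events". What remains true is that none of these is a required direct question about ideation.

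Nor can one infer that depressed mood goes unrated. The protocol says: "Occurrences of lightheadedness, dizziness on standing, palpitations, drowsiness, nausea, nasal congestion, peripheral edema, worsening of HA, and other adverse effects will be rated". The eight named effects are physical, but the list is open-ended and the rating form is not in the documents.

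Finally, the point should not be read as a claim that prazosin causes depression. It is listed at 1-4%, but the prior trial reported more Ham-D improvement on prazosin (5.3 against 0.7, p=0.07).

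**Conclusion.** The point holds as a gap in wording that should be closed. Under the rule as written, a participant seen remotely from T1 to SD2 has no required ideation question and no PHQ-9 for a nominal 9 to 11 weeks, over 6 to 8 visits and all six dose increases. This rests on reading section 5.1 literally and on those visits being remote.

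In-person conduct is the default, and the question is then required at 9 of 10 (or 11 of 12) visits. The zero count is the extreme case in which every visit is remote, not a description of the trial. The documents do not say how many participants are seen remotely, so the number affected cannot be estimated. Applying the listed 1-4% to about 107 prazosin participants (160 × 2/3) gives roughly 1 to 4 people, but that would count depression reactions over the whole trial, not missed ideation, and it does not measure this gap.

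The matter is participant safety. It does not affect the primary analysis, the power or the type I error.

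**What to change.** Reword the sentence in section 5.1 so that suicidal ideation is asked at each in-person visit and at every scheduled visit after the first dose, whether in person, by telehealth or by telephone, with the same risk assessment if it is endorsed. The requirement then covers 10 of 10 (or 12 of 12) scheduled visits after the first dose, whatever the mode.

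The cost is an amendment of one sentence submitted to both sites' IRBs and a few minutes per remote visit. A clinician able to carry out the risk assessment must also be reachable during remote visits. The on-call provision does not by itself guarantee this, because it speaks of trained personnel receiving calls and does not say that they can assess suicide risk.

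Naming depressed mood among the rated effects, or adding PHQ-9 administrations during titration, would be a matter of preference and is not needed to close this gap.

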A research monitor at Madigan will be appointed by the Madigan IRB per DoD requirements. The Research Monitor may not be a member of the study team but may be a member of the Data Safety Monitoring Board (DSMB). Duties of the Research Monitor include (but are not limited to): a) Monitoring the conduct of the protocol per the approval plan and ensuring protection of human subjects. This may involve periodic review of medical records of enrolled subjects and the research files being maintained by the PI. b) Reviewing and keeping abreast of adverse events and protocol deviations that occur during the research and c) If there is concern about the welfare of enrolled subjects, the Research Monitor has the authority to stop a research study in progress, remove individual subjects from a study, and take whatever steps necessary to protect the safety and well-being of research subjects until the Madigan IRB can assess the Research Monitor's report. Notification of such actions must be forwarded to the Madigan IRB via Madigan Department of Clinical Investigation (DCI) within one (1) working day of receipt of knowledge of actions prompting human subject welfare concerns. Any report of the Research Monitor will be forwarded to the Madigan and VA Puget Sound IRBs.

In addition to the Research Monitor, a DSMB will be established for this study, and will meet periodically following study completion by 40, 80, 120, and 160 participants. Data will be prepared for review by the DSMB by the study Data Manager. At each DSMB meeting, the safety profile of the study will be reviewed. Periodic reports following each meeting will be provided by the DSMB Chair to the PI and the IRBs. The DSMB will 1) review un-blinded data, as needed during the trial; 2) identify problems relating to safety during the study; 3) identify needs for additional data relevant to safety issues, and request these data from the study investigators; 4) propose appropriate analyses and periodically review developing data on safety and endpoints; and 5) consider the rationale for continuation of the study, with respect to progress of randomization, retention, protocol adherence, data management, safety issues, treatment efficacy, and outcome data, and make recommendations for or against the trial's continuation.

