### **5.2 Recruitment Methods**

**Description of the Recruitment Process:** Recruitment will be based on convenience sampling using available participants from Madigan/JBLM and VA Puget Sound. We anticipate enrollment of 228 participants to achieve 160 randomized -- an average of approximately 4-5 participants randomized per month divided approximately equally across the 2 sites.

At VA Puget Sound, participants will be recruited via referrals from VA outpatient clinics, including Neurology, Primary Care, Mental Health, Neuropsychology, Rehabilitation Medicine, Deployment Health, Polytrauma, and others; periodic, informational e-mail to providers and clinics summarizing the study, eligibility criteria, study PI, study staff contact information, and instructions for proper referral of potentially eligible participants; VA community-based outpatient clinics (CBOCs); local area Veterans centers; National Guard and Reserve units; hospital health fair and hallway information tables; public outreach presentations; posted IRB-approved advertising in highly trafficked areas **and** clinic waiting rooms; advertisements in newsletters, local newspapers, radio, and the Internet (including social media); presentations to appropriate clinical services (such as grand rounds presentations or service staff meetings); e-mail and presentations to local non-VA providers and community groups (e.g., TBI support groups); and word-of-mouth.

Similar recruitment strategies will be employed at Madigan/JBLM on and off-site facilities, with the addition of the TBI Program, the Warrior Transition Battalion, educational outreach to the brigades, JBLM Family & Morale, Welfare & Recreation Facilities, JBLM Education Center and a large banner at the gates into JBLM.

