#### 5.6 Data Analysis

**Sample Size:** Our estimate of required sample size for the primary outcome is based on previous studies of chronic migraine HA, which reported standard deviations for change from baseline at 16 weeks in number of migraine days/month on the order of 5-6 days for both placebo and active drug groups, and a difference in change from baseline at 16 weeks in mean number of chronic migraine HA days/month between treatment groups of about 4 days (i.e., an effect size of about 0.67). An inclusion criterion for these studies was a minimum of 15 HA days/month, whereas the corresponding inclusion criterion for our proposed study is a minimum of 8 HA days/month. We therefore may see a smaller effect size. A trial with 111 completers (74 in the prazosin group, and 37 in the placebo group) yields 80% power to detect an effect size of 0.57 for a difference in change from baseline based on a standard two-sample t-test using a two-sided 5% Type I error level. Because we will be using linear mixed effects models to analyze this outcome, our power should be greater than 80% to detect an effect size of 0.57.

To arrive at the required number of participants to randomize, we are assuming a 30% dropout rate during the Titration and Steady-Dose Periods, based on the experience of Study Consultant [name] in other HA trials in the active-duty SM population. This dropout rate is due mainly to service-related events, such as reassignment or deployment, rather than to adverse drug effects. With a 30% dropout rate, we will need to randomize 160 participants who have met all eligibility criteria. Conservatively assuming a screen-fail rate of approximately 30% based on the Pre-Treatment Screening (e.g., meeting inclusion criteria for HA frequency/severity, adequate compliance with log keeping, voluntary study withdrawal, etc.), 228 potential participants will need to be recruited and enrolled to provide sufficient participants randomized for completion of the study.

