#### 5.7 Withdrawal of Subjects

**Study Completion or Discontinuation and Breaking the Blind:** Study completion refers to an enrolled participant having completed the full 12 weeks at the constant study drug maintenance dose level. Study discontinuation refers to premature exit from the study by a participant, either voluntarily or at the recommendation of the clinician prescriber.

The clinician prescriber may authorize premature discontinuation of participant involvement for safety reasons or other concerns, discovery of use of excluded medications, or intolerable worsening of existing HAs. Participants who begin any new scheduled prophylactic headache treatment during the study will be discontinued.

The team at the study site will triage any participant to emergency care, mental health support, or clinical care/follow-up as appropriate at any time during the study.

Safety concerns leading to termination of participant involvement may include but are not limited to pregnancy, development of an intolerable adverse reaction to the study drug or inactive constituents, development of an acute serious medical condition, or development of an unstable psychiatric condition. Study discontinuation will also occur if there are unacceptable adverse effects on the lowest study drug dose (1 mg qhs). For the purpose of maintaining participant safety, physical and neurological examinations and urine pregnancy test verification will only be conducted via approved telehealth applications or during an in-person visit. If a participant is unable to comply with these restrictions, then they will be withdrawn or excluded from the study for safety reasons. The reasons for early withdrawal or discontinuation will be recorded. For participants who are prematurely discontinued from the study after randomization, we will attempt to schedule an early termination visit. At this visit, all end-of-study procedures will be obtained in order to include these measures in the Intent-to-Treat (ITT) analyses.

The blind will be broken for participants who are discontinued from the study, whether by voluntary withdrawal or on the advice of the clinician prescriber, on the date of discontinuation.

All reasons for breaking the blind will be recorded, as will the name of the person breaking the blind.

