For participants completing the entire trial, the blind will be broken at the end of the 12-week Visit. Maintaining the blind until all participants have completed the protocol and the database has been locked would be ideal; however, previous studies have shown that optimal safety and follow-up patient care argues in favor of breaking the blind for each person when they complete the trial. All participants will be given the option of treatment with open-label prazosin after study completion (an important condition for recruitment, given that prazosin is clinically available). The appropriate and safe method for initiating open-label prazosin differs depending on whether the participant had been randomized to prazosin or placebo. For those randomized to prazosin and having improvement in their HAs, subsequent open-label prazosin should be kept at the maximum achieved dose, and may be titrated further upward, if additional clinical benefit might be obtained. On the other hand, participants randomized to placebo will require titration to effect, as per the study titration schedule, initiated at a low dose (1 mg) to avoid the risk of first-dose hypotension.

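### DSMB meetings are tied to 40, 80, 120 and 160 study completions, but the plan expects only about 112 completers from 160 randomised

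*Combined protocol and SAP*

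**What the plan says.** In section 5.1, under Risk Management and Emergency Response, the DSMB "will meet periodically following study completion by 40, 80, 120, and 160 participants". The safety profile is reviewed at each meeting. The board's remit also covers retention and whether the trial should continue.

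Section 5.7 defines the term used for the trigger: "Study completion refers to an enrolled participant having completed the full 12 weeks at the constant study drug maintenance dose level". The next sentence puts early leavers in a separate category: "Study discontinuation refers to premature exit from the study by a participant, either voluntarily or at the recommendation of the clinician prescriber". The same section links completing the whole trial to the final visit: "For participants completing the entire trial, the blind will be broken at the end of the 12-week Visit".

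Section 5.6 (Sample Size) needs 111 completers, 74 on prazosin and 37 on placebo, and then states: "With a 30% dropout rate, we will need to randomize 160 participants who have met all eligibility criteria". Section 5.2 expects "an average of approximately 4-5 participants randomized per month".

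**The concern.** The highest trigger equals the number randomised, yet it is expressed in completions, and the plan expects 30% of those randomised not to complete. Under the protocol's own definition, the last two scheduled meetings would not be expected to take place.

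The wording also acts in the wrong direction. Participants who discontinue do not advance the count, so the higher the dropout, the later the board meets, although retention is one of the things it is asked to consider. These are the only DSMB meetings the protocol schedules.

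**Working it through.** **Inputs.** Randomised: 160. Dropout during titration and steady dose: d = 30%. Completers needed: 111 (all section 5.6). Triggers: 40, 80, 120, 160 (section 5.1). Accrual: r = 4–5 randomised per month (section 5.2). Time on study: 5–7 weeks of titration plus 12 weeks at steady dose (section 5.1) = 17–19 weeks, or m = 3.9–4.4 months.

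**The plan's own figures reproduce.**
- 74 + 37 completers, effect size 0.57, two-sided 5% t-test: power 0.801, against 80% stated.
- 111 / 0.70 = 158.6, so 159, against 160 stated.
- 160 / 0.70 = 228.6, against 228 enrolled.

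The sample-size arithmetic is sound. The conflict is between it and the DSMB triggers.

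**Expected completers.** 160 × 0.70 = 112. The 120 trigger exceeds this by 8. It is met on average only if dropout is at most 1 − 120/160 = 25%. The 160 trigger requires 0% dropout.

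**Chance of reaching the 120 trigger**, with completers X ~ Binomial(160, 1 − d), which assumes independent dropout:

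| Dropout d | Expected completers | P(X ≥ 120) |
|---|---|---|
| 20% | 128 | 0.950 |
| 25% | 120 | 0.542 |
| 30% (planned) | 112 | 0.096 |
| 35% | 104 | 0.004 |

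The chance of 160 completers is effectively nil in every row (1.6 × 10⁻²⁵ at 30%). The 20–35% range is an assumption made to show sensitivity.

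**When reviews would fall, counting completers only.** With constant accrual, the k-th completion comes when about k/(1 − d) + r·m have been randomised. Here r·m runs from 4 × 3.9 = 15.6 to 5 × 4.4, about 21.8 before rounding m. At d = 30%:
- k = 40: 57.1 + (15.6 to 21.8) = 73–79 randomised.
- k = 80: 114.3 + (15.6 to 21.8) = 130–136 randomised.

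At 20% dropout these become 66–72 and 116–122. At 35% they become 77–83 and 139–145.

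**When reviews would fall, counting completed or discontinued.** The k-th exit comes when between k + (1 − d)·r·m (all dropouts leave at once) and k + r·m (all leave at the end) have been randomised. At d = 30% this gives 51–62, 91–102 and 131–142 randomised for k = 40, 80 and 120. Over 20–35% dropout the ranges barely move: 50–62, 90–102 and 130–142. The 160th exit is the last participant leaving.

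**Difference in time at d = 30%.** Months earlier = k(1/0.70 − 1)/r + (0 to 0.3m).
- First review: 17.14/5 = 3.4, up to 17.14/4 + 1.3 = 5.6 months.
- Second review: 34.29/5 = 6.9, up to 34.29/4 + 1.3 = 9.9 months.

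**What does not improve.** The interval from the last in-trial review to the last participant's exit is (160 − 114.3)/r = 9.1–11.4 months when completers are counted. When exits are counted it is 40/r + (0 to 0.3m) = 8.0–11.3 months. That is no material change.

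**The case against.** The strongest reply is that the sponsor meant participants who have finished with the study, however they left. The triggers are exact quarters of 160, the DSMB paragraph does not cite section 5.7, and nobody planning for 30% dropout would knowingly schedule a review at 160 full completers. The protocol also uses completion loosely elsewhere, for instance on contraception in section 5.1 and for the trial as a whole in section 5.6. On that reading all four meetings occur, nothing is lost, and the time differences above are zero.

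This is plausible as to intent, but it does not remove the conflict. The DSMB sentence uses the term that section 5.7 defines, and section 5.7 places early leavers outside it. Whoever prepares the DSMB data could follow either reading and arrive at a different meeting schedule.

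It is also fair to say that the practical harm is limited, and this stands:
- The DSMB is told of serious events, unexpected related events and unanticipated problems as they arise (section 6.0). It may look at unblinded data when needed and ask for more safety data (section 5.1).
- The Research Monitor can stop the study, and the IRBs receive annual summaries.
- On dropout, section 5.6 says: "This dropout rate is due mainly to service-related events, such as reassignment or deployment, rather than to adverse drug effects".
- The fourth meeting, counted by exits, is a closing review, so the loss while the trial is running is one review, not two.

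**Conclusion.** The concern holds as a minor inconsistency between sections 5.1, 5.6 and 5.7. Read with the protocol's own definition and its own 30% dropout, the rule delivers two of the four stated DSMB reviews. Expected completers are 112, the 120 trigger has about a 10% chance of being reached, and the 160 trigger has effectively none.

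The count of 112 follows directly from the plan. The probability rests on independent dropout and is sensitive to the rate: at 20% dropout the 120 meeting would probably occur. The timing figures also assume constant accrual and matter only if the strict reading is applied. No interim efficacy test, power figure or primary analysis depends on these meetings.

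**What to change.** Reword the DSMB sentence in section 5.1 along these lines:

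> The DSMB will meet after 40, 80, 120 and 160 randomized participants have either completed or discontinued the study; each report will cover all randomized participants, including those who discontinued.

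This uses the two categories section 5.7 already defines. Once the planned 160 are randomised, every trigger is reached whatever the dropout. It gives three reviews while the trial is running plus a closing one, and the schedule hardly depends on the dropout rate. If the sponsor intended a different count, that should be stated explicitly and reconciled with sections 5.6 and 5.7.

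The cost is one protocol sentence and the four meetings already planned, instead of the two expected under the current wording.
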